Activation of the assigned app on the participant's smartphone will be conducted by entering the login code sent to them in their trial enrollment email. Personal information collected from the apps is limited to a first name and optional email in the ACT version of the app. The apps send, via 256-bit SSL encryption, participant-specific utilization data from smartphones to secured Fred Hutch servers: (1) # of times app was

opened, (2) specific features used, and (3) tracking of smoking and exercise practice (iCanQuit only). These data are identified by alphanumeric IDs only. Fred Hutch Shared Resource programmers will be the only persons with the ability to re-identify study participants based on the alphanumeric IDs. There will be secured backup and half-yearly risk assessment and mitigation.

Follow-up surveys data collection procedures.

For trial integrity, the follow-up data will be collected by our survey research unit that will be (1) blind to random assignment and (2) collecting cessation outcome data outside of the intervention apps. At each follow-up, we will send reminder letters using an "Address Service Requested" envelope, for automatic forwarding to new mailing addresses. Each follow-up survey and Internet tracking will collect address information. The online-telephone-mailed sequence data collection protocol is as follows: 1) Three email attempts to complete the online version of the survey; 2) Eight attempts to complete a **telephone** version of survey (one call per day from a trained surveyor); 3) Send a paper version of the survey via **US mail**.

Based on our ACT smartphone pilot RCT experience, we conservatively estimate this protocol will yield 84% retention. And to further boost retention, we will make the following protocol enhancements at all follow-up points: (1) mail a \$2 pre-incentive letter (noncontingent incentives increase retention [88]) 2 weeks before the first online survey invitation (i.e., Day -14); (2) provide a \$10 incentive for completing the online survey within 24 hours [89]; and (3) send a second copy of the **mailed** survey 2 weeks after the first mailing.

Telephone administration of the surveys will be conducted by trained staff. If the staff member gets voicemail, a short and simple message will be given letting the participant know the purpose of the call and encouraging him/her to call the study's toll-free number. Mailed surveys will include a letter inviting participants to complete the survey, a printed survey form, a self-addressed-stamped-return-envelope for the completed survey.

Potential risks to participants

The main risk to participation in this study is a small risk of breach of confidentiality. A breach could possibly occur if, for example, an unauthorized person accesses the study's database records and/or hard copy records, telephone survey conversations are accidentally overheard by someone who does not know the participant smokes or is taking part in a smoking cessation study. Also, some participants might feel emotional upset during their assigned intervention or embarrassment when talking about their smoking during the telephone surveys. Finally, some smokers making quit attempts may experience some short-term discomfort associated with nicotine withdrawal. Participants will be fully apprised of all anticipated risks in the informed consent and other intervention materials.

Protection against risk

All research activities will be reviewed and approved by the IRB at Fred Hutch to ensure that participants are adequately protected against risk. The research aims and activities, as well as risks and benefits, will be explained in detail to all potential participants prior to obtaining informed consent. Steps to protect against risk are described below:

Protection against breach of confidentiality: How survey data are processed and stored in HIPAA compliant server

All survey data records are stored in secured HIPAA compliant servers or in locked file cabinets inside locked (limited access) rooms in our secured building. Completed paper surveys have no identifying information other than the participant's unique Study ID number. Access to paper and electronic study data and records, and to the link between participant names and Study ID numbers, is restricted to a limited number of need-to-know study personnel, and data may not be taken off the premises for any purpose. Users have no access to project computers unless they have a domain (network) account. All users must change passwords every 120 days. The electronic database resides on a server that is in a locked cabinet in a locked server room, with strictly limited, key-card access. The server also lies behind Fred Hutch's firewall, which permits no access to the server at all from outside Fred Hutch, except through the database server port using a secure, encrypted channel. The research group places additional restrictions, through DBMS software, on which data items users may view and the kinds of activities they are permitted. These permissions are based strictly on each staff member's need to see and use the data. No staff member will be able to access the data by default. The Project web server also resides in the same secure room as the database server, and is similarly protected by firewalls, with no user access except through the web server software. The database administrators maintain a rigorous system of daily full tape backups of the database and web servers. The backups include sets of tapes stored at a secure distant site.

Study participants will be recruited using a publicly accessible web site running on the Apache web server on a Linux operating system. The public web server is segregated from the rest of the Fred Hutch network within a DMZ (demilitarized zone). After indicating interest in the study, participants will complete online surveys via the 256-bit secure sockets layer protocol (SSL). Employment of the SSL protocol will prevent anyone from intercepting data passed between the end user's web browser and the web server. Once randomized, each treatment group will have access to their assigned smartphone application protected upon successful download.

Surveys are implemented using a secure, metadata-driven system designed and tested by our software development team, which has been in use for the past five years for other research studies in which participants enter information about themselves. Surveys are hosted on a Web site running on the Apache web server on a Linux operating system. The public web server is segregated from the rest of the Fred Hutch network within a DMZ (demilitarized zone). Study participants who complete these online surveys will only have access to data that they have entered on in-process surveys. Participants may access partially completed surveys via a participant-specific link provided by email and entry of the participant's birthdate. Once surveys are complete, the data are inaccessible from the data collection web site. Participants and others will be prevented from accessing any other data on the Web server by a number of operating system, web server, and application controls. Users will connect to the web site to complete the surveys using the secure sockets layer protocol (SSL). Employment of the SSL protocol will prevent anyone from intercepting data passed between the end user's web browser and the web server.

Protection against emotional upset or embarrassment.

If participants feel uncomfortable answering research questions or participating in their assigned intervention they will be able to skip any assessment items that they are not comfortable answering. Participation during the intervention will also be voluntary. Participants may choose not to participate in any components of their assigned intervention which make them feel uncomfortable. All participants will have the option of contacting via email the PI, [name], a Licensed Clinical Psychologist with the experience and expertise to responding effectively to potential adverse emotional reactions. He will plan to respond within 24 hours. If a referral to treatment is needed, he is acquainted with appropriate referral facilities and processes of identifying treatment available throughout the United States.

Protection against discomfort of nicotine withdrawal.

Participants who quit smoking may experience some discomfort associated nicotine withdrawal. Participants will also be fully informed of the symptoms of nicotine withdrawal during the informed consent process. Interventions in all treatment arms provide strategies designed to cope more effectively with symptoms of nicotine withdrawal. Finally, participants in both treatment groups will be given information on pharmacotherapy for smoking cessation (e.g., nicotine patch) and how to obtain these medications.

Reporting breaches and complaints

Taken together, these measures will minimize risks to study participants. However, should a breach/complaint occur, or if a participant is not pleased with any of the surveys, or with the study's procedures, the study's scientific staff will attempt to address the concerns; if unsuccessful, the breach/complaint will be reported to the IRB office, and the participant will be referred to the Fred Hutch IRO Director.

Potential benefits of the proposed research to the subjects and others

Successfully assisting people who smoke to quit would have significant positive benefits to their health. Overall, participants assigned to any of the three interventions have the potential to benefit by quitting smoking and the potential short and long term health benefits of quitting.

Importance of knowledge to be gained

As millions of people are choosing smartphone apps to help them quit smoking, this innovative study shows exciting promise for improving the success rates of quit smoking apps and thereby lowering healthcare costs and reducing premature tobacco-related deaths.

Inclusion of women and minorities

The population for this study will be 2500 adult male and female daily smokers who want to quit smoking. Recruitment and eligibility screening methods are designed to achieve a broad representation of adult smokers, including 70% female and 30% racial/ethnic minority.

Inclusion of children

This is a study of adult smoking cessation; participants will be aged 18 or older. The NIH definition of children includes young adults up to age 21. By the NIH definition, the only “child” participants in this study will be those aged 18-21, over the age of majority and fully capable of participating in informed consent. Therefore, no special protections are required for their inclusion in this research.

Children under the age of 18 will be excluded on the basis of the following: (1) Both interventions used in this trial have not been designed for or tested with adolescent smokers; (2) Youth may respond differently to intervention than do adults. As such, data collected from these individuals may not generalize to the larger adult population; and, (3) Our standardized assessment measures were validated in adult samples and are not applicable to children.

Data safety and monitoring plan

Upon funding, the DSMP will be submitted for review by the Fred Hutch Institutional Review Board. The DSMP includes plans for the following required elements: (1) monitoring the progress of trials and safety of participants, (2) assuring compliance with requirements regarding the reporting of adverse events, (3) assuring that any action resulting in temporary or permanent suspension of the trial is reported to the sponsor, and (4) ensuring data accuracy and protocol compliance. The trial’s DSMP will be carried out by the scientific/management team, including the Principal Investigator, at weekly meetings.

Data Management

In addition to and in combination with meeting HIPAA regulations, data collected and managed will be securely handled to prevent unauthorized access or modification. All those in the study staff who have access to data on those screened and/or participating in the study will follow these procedures when handling the data: (1) education about the need for security and confidentiality, (2) signing a confidentiality agreement, (3) using passwords to control access to the electronic databases and regular changing of passwords, (4) keeping paper versions of surveys and any other paper versions of screened/participating individuals’ data in a locked room, & (5) servers will be protected by firewalls, McAfee Virus Scan Enterprise anti-virus software, daily full tape backups stored in a locked room, and encryption via the https protocol.

Data Accuracy

Data accuracy has two aspects in this trial: (1) accuracy of self-reported data by trial participants, and (2) accuracy of data management. The trial has procedures for both, which will be reviewed annually by the Project Manager and approved by the Principal Investigator.

Monitoring Data Quality and Integrity

Several procedures will be used to maintain data integrity. All databases will be stored in a centralized location at Fred Hutch on a secure server. Data will be backed up daily and access will be password protected and limited to persons working on the

project. Persons will only have access to specific data required for their project tasks. Identifying information will be stored separately from the assessment data. Data will be audited on an ongoing basis to ensure confidentiality safeguards are being maintained and data integrity is being maintained. Data entry systems will be set-up to allow field checks, range checks for continuous variables, valid value checks for categorical variables, and checks for logical consistency of responses. Queries and data reports will be generated on a routine basis to monitor data quality.

Guidelines for Monitoring and Reporting Unexpected and Adverse Events

Monitoring

Throughout the study, the Principal Investigator, Co-Investigator, and Project Manager will monitor participants for adverse events and protocol compliance. The project manager will complete monthly reports on participant progress and status, any adverse events, and any protocol deviations. Protocol adherence will be monitored by the Principal Investigator.

Reporting

Study staff will be trained, and required, to report all unexpected and adverse events to the Principal Investigator. Adverse events beyond what would be expected in the course of smoking cessation will be reported to the Fred Hutch's IRB in accordance with Fred Hutch policy.

Definitions

In general, unexpected events (UEs) include any event, adverse or otherwise, that was not described as part of the study risks. For this trial, an example of an unexpected event that is not adverse is a participant who has become very unhappy with trial procedures. Adverse events (AEs) are any untoward occurrence with a trial participant whether or not it can be considered to be related to their smoking cessation. An example of an adverse event in this trial could include an increase in depressive symptoms. Serious adverse events (SAEs) include any AE that results in death, a real risk of dying, inpatient hospitalization, persistent or significant disability/incapacity, or AEs that require intervention to prevent permanent impairment or damage. In this trial, an example of a serious adverse event would be a suicide attempt.

UEs, AEs, and SAEs will be reported to the Principal Investigator as soon as staff members are aware of them. If there is any doubt as to whether an event qualifies as a UE, AE, or SAE, staff members will be trained and encouraged to err on the side of caution – and to bring the event to the Principal Investigator's attention for review.

Attribution

The Principal Investigator, in consultation with the Co-Investigators, will decide if a UE should be classified as an AE. If an event is classified as an AE, further attribution will be determined, as follows:

- Related – AEs that are definitely, probably, or possibly related to the smoking cessation intervention.
- Not Related – AEs that are doubtfully related or clearly not related to the smoking cessation intervention.

Reporting

1. **SAE's:** For AE's meeting the criteria for an SAE, regardless of its attribution, a Fred Hutch SAE Report form will be completed. The SAE Report form will be faxed by the Principal Investigator to the IRO office at [contact] within 24 hours of the internal report. All available information will be submitted. Should additional information become available after the initial report, a revised report will be submitted within 15 days.
2. **AE's that do not meet the criteria for SAE:** For these events, the Principal Investigator or the Study Coordinator will complete and submit a Fred Hutch Adverse Event Reporting form within ten (10) calendar days of learning of the events.
3. **UE's that do not meet the criteria for AE's:** For these events, the Study Coordinator will complete and submit a Fred Hutch UE Reporting Form within ten (10) calendar days of learning of the events.

Complying with Trial Suspension Reporting Requirements

Were the Fred Hutch's IRB or Clinical Trial's Office to issue a temporary or permanent suspension of the trial, the trial's Principal Investigator will immediately contact the trial's project officer. A Data Safety Monitoring Board will not be required since this is a minimal risk behavioral intervention.

REFERENCES

1. U.S. Department of Health and Human Services. The Health Consequences of Smoking--50 Years of Progress: A Report of the Surgeon General. . In: US Department of Health and Human Services CfDCaP, National Center for Chronic Disease Prevention and Health Promotion, Office of Smoking and Health editor. Atlanta, GA2014.

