Randomized trials on apps that follow the US Clinical Practice Guidelines (USCPG) begin to address that research gap. But only following the USCPG has had limitations in other modalities of delivery [9-15]. An approach, called Acceptance & Commitment Therapy (ACT), addresses these limitations with both innovative intervention content and highly promising results from six published trials [16-21]. ACT's innovation is its dual focus on increasing willingness to experience physical cravings, emotions, and thoughts that cue smoking while making values-guided committed behavior changes [22]. We recently developed the first ACT app for smoking cessation, called "SmartQuit," and tested it in a pilot randomized controlled trial (N = 196), comparing it with an app that follows USCPG (National Cancer Institute's "QuitGuide"). The trial design was proven feasible, with successful national recruitment (N = 196 recruited in 10 weeks) and strong outcome survey completion rate (84%). Results showed that SmartQuit had: (1) higher participant engagement and satisfaction than QuitGuide, (2) higher levels of acceptance of cravings than QuitGuide, and (3) descriptively higher quit rates (albeit non-significant) than QuitGuide at the two-month follow-up [21]. Building on these promising results, we propose a fully-powered, randomized controlled trial that compares a refined version of SmartQuit, called iCanQuit to QuitGuide, which follows the USCPG, to definitively determine whether an ACT app is more efficacious than a USCPG app. Thus we propose the following Specific Aims:

Aim 1. Determine whether iCanQuit produces significantly higher abstinence than QuitGuide. **Primary endpoint:** 30-day point prevalence abstinence at 12 months post-randomization. Importance of this aim: will determine the quit rates with precision and whether iCanQuit provides more robust quit rates than QuitGuide.

Aim 2. Determine whether the iCanQuit (but not the QuitGuide) smoking cessation outcomes are mediated by these psychological processes central to the theoretical model underlying ACT: commitment to quitting and acceptance of internal (a) sensations, (b) emotions, and (c) thoughts that cue smoking. Importance of this aim: will identify ACT processes needing further targeting, and determine whether iCanQuit, but not QuitGuide, operates through ACT-specific theoretical processes.

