Aim 3. Determine whether iCanQuit is significantly more cost-effective than QuitGuide, as measured by cost per additional quitter, incremental cost-effectiveness ratio (ICER), and incremental cost per quality-adjusted life year (QALY). Importance of

this aim: will provide payers (e.g., insurance companies) and policymakers results needed to decide whether to adopt iCanQuit.

[figure not shown]
Exploratory Aim: Explore whether iCanQuit, as compared to QuitGuide, has higher quit rates for those with these baseline factors: (a) low acceptance of sensations, emotions, and thoughts that cue smoking, (b) heavy smoking (≥ 20 cigarettes/day), (c) current mental health symptoms, and (d) being racial/ethnic minority. Importance of this aim: will potentially identify key subgroups that benefit most from iCanQuit, and thereby aid in reducing tobacco-related health disparities.

Innovations. (1) ACT's innovative features augment the US Clinical Practice Guidelines; (2) ACT follows an innovative theory: Relational Frame Theory; (3) ACT on the smartphone is novel; (4) First randomized trial of a smartphone app for adult smoking cessation; (5) The first time that the following have been tested for **any** behavior outcome: (a) ACT delivered via smartphone, (b) mediation of the effects of a smartphone app, (c) cost-effectiveness of a smartphone app, and (d) exploration of subgroups who benefit most from a smartphone app. While there are thousands of apps and hundreds for smoking [2], testing an app's efficacy is scientifically innovative. That's a critical gap this application fills.

Approach

Randomized trial experimental design. We will conduct a fully-powered two-arm randomized controlled trial that compares iCanQuit to QuitGuide, which follows the USCPG. To balance baseline variables between the two conditions, we will stratify randomization by daily smoking frequency (≤ 20 vs. ≥ 21), education (\leq high school vs. \geq some college), race/ethnicity (minority race/ethnicity vs. non-Hispanic White) and depression screen (CES-D score ≤ 15 vs. ≥ 16). Moderators will be measured at baseline. Mediators will be measured at baseline and three months post randomization. Consistent with cessation trial designs [60], cessation and cost-effectiveness outcomes will be measured at 3, 6, and 12 months post randomization.

Figure 1. Experimental Design

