Analyses. Aim 1. Our primary outcome hypothesis is that iCanQuit will have significantly higher 30-day point prevalence abstinence at 12 months post-randomization than QuitGuide. **Analyses:** For each comparison of the arms on the primary and all secondary endpoints, we will use a logistic regression model with complete case smoking cessation outcome [9-14]. The model will adjust for all stratification factors as well as baseline factors that might be imbalanced after randomization. In addition, we will conduct these analyses: (1) multiple imputation of missing outcomes [90-92], (2) missing equals smoking outcomes [9-14], (3) using a secondary cessation outcome of no use of cigarettes **and** other nicotine or tobacco products except FDA-approved nicotine replacement therapies. Finally, we will compare the two arms on utilization of their assigned app.

Aim 2. We hypothesize that the iCanQuit arm's (but not the QuitGuide arm's) smoking cessation outcomes will be strongly mediated by these psychological measures that are central to the theoretical model underlying ACT: commitment to quitting and acceptance of internal (a) sensations, (b) emotions, and (c) thoughts that cue smoking. This hypothesis is consistent the ACT model and prior ACT for smoking cessation intervention studies [16, 17, 20, 82]. **Analyses:** For each mediator, the model is expressed as three regression equations that relate the main independent variable X

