(ACT intervention), the mediator M (change from baseline to 3-months post randomization in the acceptance variable, and/or commitment to quitting smoking despite internal cues), and the binary endpoint Y at 12-months post-randomization (e.g., 30-day abstinence). The first regression describes the total intervention effect (X) on the outcome (Y): $\text{logit}(Y) = \gamma_1 + \tau X$, where the parameter τ measures the total intervention effect. The second regression describes the impact of the intervention (X) on the mediator (M): $M = \gamma_2 + \alpha X$. The third regression describes the simultaneous impacts of the intervention (X) and mediator (M) on the outcome (Y): $\text{logit}(Y) = \gamma_3 + \tau'X + \beta M$. Since the endpoint is binary, the mediation effect is the product term $\alpha\beta$, whose empirical distribution will be estimated via 5000 bootstrapped samples. Bootstrapping is a resampling method which provides a powerful test of mediation that does not rely on normality assumptions [93-95]. Randomization should remove potential confounding effects [92, 93], and if needed, we will adjust each model by covariates that differ at baseline or predict outcome. Following VanderWeele and Preacher methods [94, 95], we will also explore any interactions between mediators and treatment arm. And we will explore whether utilization of assigned app and usage of cessation pharmacotherapy mediates cessation outcomes.

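### Aim 2 claims that ACT processes mediate outcomes under iCanQuit and not under QuitGuide, but the planned between-arm product αβ can only test whether iCanQuit's advantage over QuitGuide is mediated

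*Combined protocol and SAP*

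**What the plan says.** Aim 2 under Significance & Specific Aims is stated arm by arm: "Determine whether the iCanQuit (but not the QuitGuide) smoking cessation outcomes are mediated by these psychological processes". Its importance statement says the aim will "determine whether iCanQuit, but not QuitGuide, operates through ACT-specific theoretical processes". The Aim 2 paragraph under Analyses repeats the contrast as a hypothesis: "We hypothesize that the iCanQuit arm's (but not the QuitGuide arm's) smoking cessation outcomes will be strongly mediated". On design, the Approach section says: "We will conduct a fully-powered two-arm randomized controlled trial that compares iCanQuit to QuitGuide". QuitGuide is an active app, and there is no untreated arm.

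The Aim 2 analysis has three equations, where X is arm, M is the mediator's change from baseline to 3 months, and Y is 12-month abstinence:

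- logit(Y) = γ₁ + τX
- M = γ₂ + αX
- logit(Y) = γ₃ + τ′X + βM

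The mediation effect is αβ, with its distribution taken from 5,000 bootstrap samples. The third equation has no X×M term. Later the same paragraph adds: "we will also explore any interactions between mediators and treatment arm". It gives no test, threshold or estimand for this and does not tie it to the statement about QuitGuide.

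The Power section gives more than 99% power at 811 per arm for mediators that explain at least 60% (acceptance) or 25% (commitment) of ACT's effect. It gives no power for a QuitGuide-specific statement, and the plan has no criterion for concluding that QuitGuide's outcomes are not mediated.

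**The concern.** The aim makes two claims: the processes operate under iCanQuit, and they do not operate under QuitGuide. The planned estimate is a single between-arm quantity. A positive αβ is evidence that part of iCanQuit's advantage runs through the mediator. It is not evidence that QuitGuide works by another route, because several different QuitGuide patterns give the same αβ.

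What is at stake is a conclusion about specificity of mechanism, which the importance statement presents as a product of the trial. The Power section labels this a primary aim. The Aim 1 endpoint, the sample size and the data collection are not affected.

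**Working it through.** **1. The plan's own figures.** Inputs from the Power section: quit rates 11% and 7%, two-sided 0.05, 80% power.

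- The pooled two-proportion formula gives 803 per arm (1,606 in total) and a logit Wald formula gives 1,634. The stated 1,622 lies between them.
- The total log odds ratio is ln(0.11/0.89) − ln(0.07/0.93) = 0.496, so αβ is 0.60 × 0.496 = 0.298 for acceptance and 0.25 × 0.496 = 0.124 for commitment.
- Approximate power is Φ(α/SEα − 1.96) × Φ(β/SEβ − 1.96), with SEα = √(2/n), SEβ = 1/√[n(0.11×0.89 + 0.07×0.93)], and mediator SD 1 (assumed).
- At n = 811, SEα = 0.050 and SEβ = 0.087. The plan does not say how αβ splits into α and β. For the 25% case, power is 52% at α = 0.1 SD, 98% at 0.2, above 99% at 0.25 to 0.3, 95% at 0.4 and 81% at 0.5. For the 60% case it is about 99% or more for α from 0.25 to 0.8.

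So more than 99% is attainable, but it refers to αβ only.

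**2. What αβ responds to (algebra).**

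- Add c to M in both arms. Then γ₂ becomes γ₂ + c and γ₃ becomes γ₃ − βc, while α, β and αβ do not change. On one simulated data set αβ was 0.3025 at common shifts of 0, 1 and 2 SD.
- Add c in QuitGuide only. Then α becomes α − c. With α = 0.5 and c = 0.5, αβ is 0.

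**3. Arm-specific patterns (simulation).** 811 per arm, 2,000 runs, quit rates held at 11% and 7%, mediator SD 1. Joint significance of α and β stands in for the bootstrap. The mean changes and slopes are assumptions, since the documents give none. Pairs are iCanQuit / QuitGuide.

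| Pattern | Mean change (SD) | True slope | Mean αβ | αβ significant | X×M significant |
|---|---|---|---|---|---|
| A | 0.5 / 0 | 0.6 / 0.6 | 0.301 | 100% | 5.2% |
| B | 1.5 / 1.0 | 0.6 / 0.6 | 0.301 | 100% | 5.7% |
| C | 0.5 / 0 | 1.0 / 0 | 0.281 | 100% | 99.9% |
| D | 1.0 / 1.0 | 0.6 / 0.6 | −0.001 | 5.0% | 5.9% |
| E | 0.5 / 0 | 0 / 1.3 | 0.233 | 99.8% | 100% |

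A and B differ by 1 SD of mediator change in QuitGuide and give the same αβ. C has the mediator–outcome link only in iCanQuit and E only in QuitGuide, yet both are declared significant almost always. In D the mediator rises in both arms and predicts quitting in both, and αβ is about zero.

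**4. What an X×M term would add.** It separates C from E. It does not separate A from B, because a common shift in M leaves both arm-specific slopes unchanged. The mean change in each arm is needed for that.

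The approximate SE of the slope difference is √[1/(n×0.07×0.93) + 1/(n×0.11×0.89)]. At n = 811 this is √(0.1376² + 0.1122²) = 0.178. The 1,050 column is 84% of 1,250 (the stated retention), and quit rates of 11% and 7% are kept throughout.

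| Slope difference (log-odds per SD) | 811 per arm | 1,050 per arm | 1,250 per arm |
|---|---|---|---|
| 0.3 | 39% | 49% | 56% |
| 0.4 | 62% | 73% | 80% |
| 0.5 | 80% | 89% | 94% |
| 0.6 | 92% | 97% | 99% |

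The difference detectable with 80% power is 0.50, 0.44 and 0.40 respectively. The 95% interval for the QuitGuide slope would be about ±0.27, ±0.24 and ±0.22.

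**The case against.** A reader might infer that αβ carries no information about QuitGuide. The documents do not support that. QuitGuide's mean change is the reference for α, and its participants contribute to β. If QuitGuide alone raised the mediator, α would fall, and pattern D shows αβ vanishing when the two apps move it equally. Invariance to a shift common to both arms is an ordinary property of a randomised contrast, and it usefully removes the natural course of a quit attempt.

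A reader might also infer that a shared slope contradicts the hypothesis. It need not. The plan does not say which path is absent under QuitGuide. Table 3 contrasts acceptance with avoidance of urges, which suggests that QuitGuide does not raise acceptance. That reading is compatible with one β.

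Three further points have force. Mediators are measured in both arms at baseline and 3 months, and a mediator-by-arm interaction is already to be explored. No rule says that a positive αβ will be reported as proof of the negative half. The active comparator is a reasoned choice, so the missing untreated arm limits inference and is not a planning error.

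What remains is narrower. The wording promises more than αβ can deliver, and the exploratory interaction does not close the gap. It tests slope differences only and is unspecified. A non-significant slope in QuitGuide would not show absence of mediation. Arm does not vary within QuitGuide, so that app's own effect on the mediator cannot be estimated.

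**Conclusion.** The concern holds in this form: the planned αβ tests whether iCanQuit's advantage over QuitGuide is mediated, and it cannot by itself support the claim that QuitGuide's outcomes are not mediated by these processes. The invariance to a common shift is exact. The 100% and 99.8% figures rest on assumed slopes, a mediator SD of 1 and a joint-significance test, so they illustrate that opposite patterns can give the same result and do not predict this trial. The stated power above 99% does not extend to the interaction. Under the same assumptions, interaction power is 39% to 92% at 811 per arm for slope differences of 0.3 to 0.6. The point affects what may be concluded from Aim 2 and leaves Aim 1 untouched.

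**What to change.** 1. Reword Aim 2, its importance statement and the hypothesis under Analyses so that the question is whether iCanQuit's advantage over QuitGuide is mediated by acceptance and commitment. Drop the clause that excludes QuitGuide.

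2. Keep αβ as the main mediation estimate. As a pre-specified secondary analysis, fit the outcome model with an X×M term for each mediator. Report the arm-specific mediator–outcome slopes and the mean baseline-to-3-month mediator change in each arm, with 95% confidence intervals. Label them as associations, since the mediator is not randomised and QuitGuide's change is mixed with the natural course of a quit attempt.

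3. State that the power above 99% does not apply to the interaction, and that a non-significant result will not be read as absence of mediation in QuitGuide.

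The cost is some rewording and one extra model per mediator on data already planned. The downside is a more modest claim and wider intervals for the arm-specific slopes.
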